#### Toxicity and safety

- Time to composite safety endpoint by Kaplan-Meier analysis.
- The number of LAM related complications (pneumothorax, chylous effusions, respiratory infections and angiomylipoma bleeding) in each group will be analysed by Chi Square test.
- The number of doxycycline related side effects (related and unrelated) in each group will be analysed by Chi Square test.

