#### Background and preliminary data

Cystic lung destruction is the hallmark of pulmonary LAM and generally results in respiratory failure over a variable period of time. Over-activity of proteases including elastase, trypsin and the matrix metalloproteinases (MMPs) is responsible for parenchymal destruction in emphysema and other lung diseases. The MMPs are a family of zinc dependent proteolytic enzymes with proteolytic activities against extra-cellular matrix proteins. The MMPs are overexpressed in inflammatory and neoplastic diseases where in addition to processing extra-cellular matrix they also have roles in metastasis, angiogenesis, growth factor activation and inactivation. MMPs -1, -2, and -9 are involved in the sequential digestion of collagen and gelatin and are strongly expressed in the walls of cysts where it is thought they contribute to parenchymal destruction in LAM. Further, MMPs can be detected by gelatin zymography in the urine of patients with LAM but not controls. Doxycycline is a tetracycline antibiotic in common clinical use. In addition to its antimicrobial action it inhibits the synthesis and activity of several MMPs and inhibits proliferation of a range of cell types including arterial smooth muscle, cancer cells and cancer model systems. In preliminary experiments we have demonstrated that primary LAM derived and angiomyolipoma cells produce MMP-2 and -7 and that MMP expression and proliferation in these cells is inhibited by doxycycline.

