### **Dose escalation of doxycycline and urine zymography.**

In order to determine the dose of doxycycline that suppresses MMP production doxycycline will be increased and urine MMPs measured. After one month doxycycline will be increased from 50mg od to 50mg bd, after two months to 50 mg tds and at three months to 100 mg bd. Patients will stay on this dose for the remainder of the study. Blinding will be maintained during dose adjustment by prescribing all patients four study tablets being a combination of 50mg doxycycline and matched placebo tablets, dose adjustment will be performed by an independent person in a double blind manner. At one, two and three months urine will be sent by post to the study centre and zymography will be performed by a person blind to the clinical details of the patient. The group has a longstanding interest in the biology of MMPs in respiratory disease and expertise in MMP analysis. In a preliminary study we have shown that urine MMPs are stable for greater than 30 hours at room temperature and can therefore be analysed at a site distant from collection (figure 1).

**Figure 1. Urinary MMPs in LAM.** Urine from three patients with LAM taking no treatment, rapamycin or doxycycline analysed by gelatin zymography after delays of 6-72 hours. MMPs are detectable in the urine of patients with no significant reduction up to 30 hours. The patient taking doxycycline has almost undetectable MMPs. LC-MMP-9: lipocalin associated MMP-9.

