### Secondary endpoints

Comparison between the two groups for:

- Rate of change of FVC over 24 months
- Change in DLCO at 12 and 24 months
- Change in shuttle walk distance at 12 and 24 months
- Change in quality of life at 12 and 24 months
- Time to composite safety endpoint
- Number of complications - pneumothorax, pleural effusions, angiomyolipoma bleeding
- Number of respiratory infections
- Adverse effects

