### Statistical analysis of endpoints

#### Primary endpoint

The primary endpoint will be the difference in rate of decline of FEV1 (ml/year) measured over 24 months.

All data will be analysed on an intention to treat basis in conjunction with the trial statistician [name]. The mean slope of regression lines for FEV1 and FVC, plus change in DLCO, shuttle walk distance and quality of life in the doxycycline and placebo groups will be compared by parametric or non-parametric analysis as appropriate following analysis of the data for normality. In addition we will perform a *per protocol* analysis of mean rate of change of FEV1/year. Time to composite safety endpoint will be analysed by Kaplan-Meier analysis, complications and adverse events by Chi Square test. Patients withdrawing from the study will continue to have measurements made where possible for intention to treat analysis. Missing values will be handled by multiple imputation.

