### **Expected adverse events related to doxycycline**

Doxycycline is a widely used antibiotic for which serious side effects are rare. The drug is absorbed by the oral route and eliminated with a half-life of 18 hours, by faecal and renal excretion. Absorption is not significantly affected by the presence of food in the stomach. Doxycycline does not accumulate significantly in patients with renal function impairment. In the blood, doxycycline is 90 % protein-bound. The usual adult therapeutic dose is 100 to 200 mg/day.

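### The analysis section pools respiratory infections into LAM complications, against the endpoint list, in a trial of an antibacterial drug, and does not fix what its chi-square test counts

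*Protocol*

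**What the plan says.** The protocol describes complications in two places.

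- Secondary endpoints: "Number of complications - pneumothorax, pleural effusions, angiomyolipoma bleeding", followed by a separate item, "Number of respiratory infections".
- Section 4, Toxicity and safety: "The number of LAM related complications (pneumothorax, chylous effusions, respiratory infections and angiomylipoma bleeding) in each group will be analysed by Chi Square test".

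The general analysis paragraph in section 4 repeats the test, "complications and adverse events by Chi Square test", without naming the unit counted. The next bullet in Toxicity and safety tests "The number of doxycycline related side effects (related and unrelated) in each group", also by chi-square.

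On the drug, Background and preliminary data states: "In addition to its antimicrobial action it inhibits the synthesis and activity of several MMPs". The dose escalation section raises the dose from 50 mg od to 50 mg bd after one month, then "after two months to 50 mg tds and at three months to 100 mg bd", and keeps it there. The section on expected adverse events of doxycycline says: "The usual adult therapeutic dose is 100 to 200 mg/day".

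**The concern.** An endpoint and its analysis should be the same variable, and here they are not. The endpoint list has three complication types with infections apart. The analysis has four types with infections inside, and a narrower effusion term.

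The difference matters because of the drug. A bacterial respiratory infection may be prevented by an antibacterial whatever happens to the cysts, lymphatics or angiomyolipomas. A category labelled as LAM complications could then move because of antibacterial action alone. In a safety table the reverse also matters: fewer infections could offset more pneumothoraces, effusions or bleeds.

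Two further faults sit in the same bullets. A chi-square test on numbers of events treats each event as independent, although one patient can have several. And a count of drug-related effects that includes unrelated ones defines no count.

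**Working it through.** **Design figure.** The protocol gives no calculation for complications. Its only design figure is 20 per group for FEV1 (70 ml/year, SD 75 ml/year, 80% power). A two-sample t-test at two-sided 0.05 needs 19.03, rounded up to 20, and 20 per group gives 82.0% power. That figure reproduces and is not in question. The checks below use 20 per group.

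**1. The two definitions side by side**

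| | Secondary endpoints | Toxicity and safety |
|---|---|---|
| Pneumothorax | in the set | in the set |
| Effusions | pleural | chylous |
| Angiomyolipoma bleeding | in the set | in the set |
| Respiratory infections | separate endpoint | in the set |

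**2. Dose.** 50 mg bd is 100 mg/day, 50 mg tds is 150 mg/day and 100 mg bd is 200 mg/day. From the end of month 1 the dose lies in the stated usual range of 100 to 200 mg/day.

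**3. Effect of pooling.** Let s be structural events per patient over 24 months (no treatment effect), i infections per patient on placebo, and r the infection rate ratio. Then

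pooled rate ratio = (s + i·r) / (s + i).

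The documents give none of these inputs. Assumed: s = 0.2 to 0.4, i = 1 to 2, r = 0.7 or 0.5. The last two columns are simulated chances of p < 0.05 in favour of doxycycline (40,000 trials, infection variance = mean + 0.5·mean²).

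| s | i | r | Pooled rate ratio | Event totals | Patients with ≥1 event |
|---|---|---|---|---|---|
| 0.2 | 1 | 0.7 | 0.9/1.2 = 0.75 | 0.18 | 0.07 |
| 0.2 | 2 | 0.7 | 1.6/2.2 = 0.73 | 0.33 | 0.08 |
| 0.4 | 1 | 0.7 | 1.1/1.4 = 0.79 | 0.16 | 0.07 |
| 0.4 | 2 | 0.7 | 1.8/2.4 = 0.75 | 0.31 | 0.08 |
| 0.2 | 1 | 0.5 | 0.7/1.2 = 0.58 | 0.38 | 0.16 |
| 0.2 | 2 | 0.5 | 1.2/2.2 = 0.55 | 0.64 | 0.20 |
| 0.4 | 1 | 0.5 | 0.9/1.4 = 0.64 | 0.33 | 0.14 |
| 0.4 | 2 | 0.5 | 1.4/2.4 = 0.58 | 0.61 | 0.16 |

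With infections removed, the same chance is 0.022 to 0.027 by either count, the nominal one-sided level. Part of the event-total column is clustering: at r = 1 it is already 0.046 to 0.079.

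Masking follows from the same formula. With s = 0.4, i = 1 and r = 0.7, infections fall by 0.3 per patient. If structural events rose from 0.4 to 0.7, the pooled ratio would be (0.7 + 0.7)/1.4 = 1.00.

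**4. If events are counted.** With no treatment effect, mean m events per patient and variance m + k·m², the chi-square on event totals has type I error of about 2·[1 − Φ(1.96/√(1 + k·m))]. Values of m and k are assumptions; simulated results are in brackets.

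| m | k = 0.5 | k = 1 | k = 2 |
|---|---|---|---|
| 1 | 0.110 (0.108) | 0.166 (0.165) | 0.258 (0.257) |
| 2 | 0.166 (0.160) | 0.258 (0.255) | 0.381 (0.376) |

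The excess has no direction: at m = 2, k = 1, 0.130 of the 0.255 favours doxycycline. A chi-square on patients with at least one event stays at 0.04 to 0.06 in these settings.

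**5. If patients are counted.** Take 4 of 20 against 0 of 20 as an illustration. The expected count in each event cell is 4 × 20/40 = 2.

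- Pearson: 40 × (4·20 − 0·16)² / (4·36·20·20) = 4.44, p = 0.035.
- With continuity correction: 40 × (80 − 20)² / 57,600 = 2.5, p = 0.114.
- Fisher, two-sided: 2 × C(20,4)/C(40,4) = 2 × 4,845/91,390 = 0.106.

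The protocol does not say which form of chi-square is meant, and at these counts the choice decides significance.

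**6. Side-effect bullet.** The adverse event procedure already sorts causality into five categories and treats possibly, probably and definitely related events as adverse reactions. The bullet's own parenthesis cancels that distinction.

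**The case against.** The other side has real points.

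- **Grouping.** The list of expected LAM events names chest infection beside pneumothorax, chylothorax and angiomyolipoma haemorrhage, so the pooled set follows the protocol's own safety list and sits under safety, not efficacy. That explains the grouping. It does not make infections interchangeable with structural events when an antibacterial is compared with placebo.
- **Transparency.** A reader might infer that a fall in infections is bound to be reported as a fall in LAM complications. The documents do not support that. Infections are also a secondary endpoint in their own right, so the source of a pooled difference could be seen. The bracketed list could even be read as types to be tested one by one.
- **Direction of clustering.** A reader might infer that repeat events also create apparent benefit. They do not; the error is symmetric. Only the pooling has a direction.
- **Unit.** The wording does not settle whether events or patients are counted. A 2×2 chi-square often counts patients, and then clustering does not arise. Unit and small-count rules are often left to a statistical analysis plan.
- **Limited repeats.** The Combined safety endpoint section withdraws patients after pneumothorax, increased chylous effusion or angiomyolipoma bleeding. Repeats would therefore come mainly from infections. These structural events also enter the Kaplan-Meier analysis of the composite, which counts each patient once and allows for unequal follow-up.
- **Evidence on infections.** The documents state antibacterial activity and dose, not prevention of respiratory infection.

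These points remove any claim of certain bias and confine the clustering issue to one reading. They leave the contradiction between the sections, the possible bias from pooling and the self-contradictory bullet.

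**Conclusion.** The concern holds in a limited form. The endpoint list and the analysis section define complications differently, and this rests on no assumption. Pooling infections could favour doxycycline, or hide a rise in structural complications, without any effect on LAM. The pooled rate ratio would be about 0.55 to 0.79 under assumed infection rate ratios of 0.5 to 0.7 and the assumed event rates above.

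The chi-square problem is conditional. On event totals, type I error is about 11 to 38% in both directions for assumed means of 1 to 2 and k of 0.5 to 2, driven mainly by infections. On patients, the type I error holds near its nominal level in the clustered settings checked, but expected counts may be too small for chi-square. The side-effect bullet defines no usable count on any reading.

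Only secondary and safety comparisons are affected. The FEV1 primary endpoint and the sample size are untouched.

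**What to change.** In Toxicity and safety:

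1. Take respiratory infections out of the LAM complication set and analyse them separately, as the Secondary endpoints list does.
2. Use one effusion term, pleural or chylous, in both places.
3. State the patient as the unit and compare patients with at least one event by Fisher's exact test. An overdispersed rate model for infections is optional. It suits the structural events poorly, because there the event itself can end follow-up.
4. Replace the side-effect bullet with two counts per arm: patients with any adverse event, and patients with any event judged possibly, probably or definitely related.
5. Bring the chi-square sentence in the general analysis paragraph and in the Summary into line.

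These are wording changes and need no new data. The cost is fewer events in the LAM complication set, and so wider intervals.

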## **2 Study aims/objectives**

### Hypothesis

Doxycycline will prevent matrix metalloproteinase dependent tissue destruction in lymphangioleiomyomatosis (LAM) thus preserving lung function, exercise capacity and quality of life.

We will perform a randomised placebo controlled trial of doxycycline on rate of decline of FEV1 over two years against matched placebo. This study will:

- (1) determine the optimum dose of doxycycline needed to suppress MMP production.
- (2) define the safety profile of doxycycline in LAM.
- (3) provide evidence for efficacy and size of effect.
- (4) provide data to help optimise the design and logistics of future trials.

With the data obtained we will be in a strong position to apply for European funding for a European wide trial should this still be required.

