### **Combined safety endpoint.**

To avoid withholding treatment from those who decline rapidly in the placebo group, patients with either a fall from baseline FEV1 of 300 ml or a fall in resting SaO2 of 3% (on two occasions) will be unblinded and offered doxycycline according to the protocol. Those deteriorating in the doxycycline group will be withdrawn from the study at the discretion of the doctor. In addition, patients with either pneumothorax, increase in chylous effusion or bleeding angiomyolipoma will be withdrawn. Patients fulfilling these criteria for withdrawal, together termed the 'composite safety endpoint', will be compared between treatment arms.

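### Intention to treat is applied to all data, adverse events included, although declining placebo patients may take open doxycycline, so reactions after a switch would be counted under placebo

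*Protocol*

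**What the plan says.** Four parts of the Protocol bear on this.

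- **Toxicity and safety:** "The number of doxycycline related side effects (related and unrelated) in each group will be analysed by Chi Square test".
- **Statistical analysis of endpoints, Primary endpoint:** "All data will be analysed on an intention to treat basis in conjunction with the trial statistician". The same paragraph names "complications and adverse events by Chi Square test" and adds "Patients withdrawing from the study will continue to have measurements made where possible for intention to treat analysis". The only other analysis set is per protocol, and it covers the FEV1 slope alone.
- **Combined safety endpoint:** patients with an FEV1 fall of 300 ml, or a resting saturation fall of 3%, on two occasions "will be unblinded and offered doxycycline according to the protocol". The Summary also gives placebo patients this option, after assessment by an independent expert, and analyses them by intention to treat.
- **Study aims:** one aim is to "define the safety profile of doxycycline in LAM". Adverse effects are listed among the between-group secondary endpoints.

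A further sentence, inside the FVC bullet under Secondary endpoints, censors patients at withdrawal, including withdrawal under the combined safety criteria. No section defines a safety set by treatment received or says when adverse events stop counting toward the randomised arm.

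**The concern.** Intention to treat protects an efficacy comparison. For harm, in a trial that moves some control patients onto the active drug, it credits reactions to that drug to the control arm. If a placebo patient starts open doxycycline and then has photosensitivity or oesophagitis, her reaction raises the placebo count, and her exposure is absent from the doxycycline column. If such reactions are truly more frequent on doxycycline, the error goes one way: the difference shrinks. Safety is one of four stated aims of a pilot meant to inform a larger trial, so the tabulated counts matter as much as the test.

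**Working it through.** **1. Inputs from the Protocol.** Group size 20 and assumed SD of FEV1 decline 75 ml/yr (Sample size). Cohort declines in the same section: 118 (SD 142), 106 (SD 143) and 75 (SD 149) ml/yr. Trigger: 300 ml fall on two occasions. Visits every 3 months to month 24. Photosensitivity 8-11% on doxycycline (Frequent adverse effects).

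**2. The Protocol's own figure.** Its only sample-size figure concerns FEV1. With two-sided 5% assumed, n = 2 × (1.96 + 0.84)² × 75² / 70² ≈ 18.0, rounded up to 19 per group. Twenty per group gives 82.0% power by the t distribution. The stated 20 is reproduced. It does not address side effects.

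**3. Share of placebo patients who could switch, no within-patient variation.** Assume normally distributed slopes, a linear fall, the FEV1 trigger only and a second visit for confirmation. To have time left on doxycycline, the patient must be confirmed by month 21, so the fall must reach 300 ml by month 18: a slope of at least 300 / 1.5 = 200 ml/yr. Share = 1 − Φ((200 − mean) / SD). Patient-time share = share × mean years left / 2; mean years left come from simulating the same model.

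| Mean, SD (ml/yr) | z | Share | Of 20 | Mean years left | Placebo patient-time |
|---|---|---|---|---|---|
| 118, 75 | 1.093 | 13.7% | 2.7 | 0.36 | 2.5% |
| 106, 75 | 1.253 | 10.5% | 2.1 | 0.35 | 1.8% |
| 75, 75 | 1.667 | 4.8% | 1.0 | 0.33 | 0.8% |
| 118, 142 | 0.577 | 28.2% | 5.6 | 0.53 | 7.5% |
| 106, 143 | 0.657 | 25.5% | 5.1 | 0.53 | 6.8% |
| 75, 149 | 0.839 | 20.1% | 4.0 | 0.52 | 5.2% |

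**4. With within-patient variation.** The Protocol gives no within-patient SD, so I take 0 to 120 ml as an assumption, applied to baseline and every visit, with any two visits counting. By simulation:

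- Protocol SD of 75: 5-32% of placebo patients (1-6 of 20) and 1-11% of placebo patient-time.
- Cohort SDs of 142-149: 20-37% (4-7 of 20) and 5-14%.

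Requiring consecutive visits lowers the 37% to 31%. Those triggered have on average about 0.3 to 0.75 year left.

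**5. Dilution.** Let c be the share switching, and p1 and p0 the reaction risks on doxycycline and placebo. The observed placebo risk is (1 − c)p0 + c·p1, so the observed difference is (1 − c)(p1 − p0). The proportional loss is c. This is an upper bound, because it gives switchers the full reaction risk despite shorter exposure.

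For photosensitivity, with p0 = 0 assumed:

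| c | Difference if p1 = 8% | Difference if p1 = 11% | Misplaced events of 20 |
|---|---|---|---|
| 0.05 | 7.6 points | 10.5 points | 0.1 |
| 0.32 | 5.4 points | 7.5 points | 0.5-0.7 |
| 0.37 | 5.0 points | 6.9 points | 0.6-0.8 |

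The last column is 20 × c × p1.

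**The case against.** The strongest reply is that the text is ambiguous. The Combined safety endpoint section treats the decline triggers as criteria for withdrawal, and the FVC bullet censors at withdrawal. If that rule reached adverse events and a switch counted as withdrawal, later reactions would drop out of the placebo count. This stands in part: the Protocol does not settle the matter beyond argument. But the rule is written for FVC, conflicts with the continued measurement promised under the primary endpoint, and is nowhere extended to adverse events.

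A second reply is that on-treatment cut-offs belong in a statistical analysis plan. That is true of the table layout. It does not excuse the Protocol's own statement that "All data will be analysed on an intention to treat basis", which such a plan could cure only by departing from it.

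A third is size. About 2 of 20 against 0 of 20, roughly what 8-11% would give, has Fisher p = 0.49 with no switching at all. This stands: the test would say little on this example either way. The misplaced count in the descriptive table remains.

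Two stronger readings are tempting. A reader might infer that safety data from switchers are lost. They are not: the adverse event procedure and form record dates, causality and action on doxycycline for each event, and the monitoring committee reviews all adverse events. A reader might also infer that the drug will certainly look safer than it is. That depends on uptake of an optional offer and on reaction rates after the switch, neither of which the Protocol gives.

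**Conclusion.** The point holds as a fault of wording with a probably modest effect. On the most natural reading, reactions after a switch to open doxycycline are counted under placebo, which biases the safety comparison toward no difference. The loss is at most the share who switch: 5-32% under the Protocol's planning SD, 20-37% under the cohort SDs. For photosensitivity that is less than one patient in 20.

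These figures assume normal slopes, a linear fall, a within-patient SD of 0-120 ml, acceptance by every eligible patient and full reaction risk after switching. The last two make the dilution an upper bound for a given number of triggered patients. Leaving out the saturation trigger works the other way, because it could add switches. Confidence in the reading is moderate because of the competing censoring sentence.

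**What to change.** Three changes of wording, none touching who is offered treatment or when.

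1. Under the primary endpoint analysis, limit intention to treat to the efficacy endpoints.
2. Under Toxicity and safety, count side effects by the treatment being taken at onset. Placebo patients contribute to placebo until their first doxycycline dose. Later events go in a separate placebo-then-doxycycline column and into a summary of all doxycycline-exposed patients with patient-time.
3. Reconcile the primary endpoint paragraph with the FVC bullet on what is counted after withdrawal or switching.

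Event onset dates are already collected; the date of the first open dose must also be recorded. The cost is one extra table and slightly less placebo follow-up in the comparison.
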